4.2. Overall Study Duration

Screening is up to 42 days (~6 weeks); the double-blind, vehicle-controlled treatment period is 24 weeks; the open-label treatment extension period is 28 weeks; and safety follow-up is 30 days. Total duration is up to approximately 63 weeks (see Figure 1).

The study will begin when the first participant (or legally authorized representative) signs the study ICF. The end of the study is defined as the date of the last visit of the last participant in the study or the date that the last participant discontinued study drug and completed applicable safety follow-up assessments or is lost to follow-up.

A participant is considered to have completed the study if he/she has completed all study visits, including the safety follow-up visit. A study is considered completed when the last participant last visit has occurred.

4.3. Study Termination

The investigator retains the right to terminate study participation at any time, according to the terms specified in the study contract. The investigator is to notify the IRB/IEC of the study's completion or early termination in writing, send a copy of the notification to the sponsor or sponsor's designee, and retain 1 copy for the site study regulatory file.

The sponsor may terminate the study electively or if required by regulatory agency. In the event of significant safety findings, the study will be terminated. If the study is terminated prematurely, the sponsor or designee will notify the investigators, the IRBs/IECs, and regulatory bodies of the decision and reason for termination of the study.

5. STUDY POPULATION

Deviations from eligibility criteria are not allowed because they can potentially jeopardize the scientific integrity of the study, regulatory acceptability, and/or participant safety. Therefore, adherence to the criteria as specified in the Protocol is essential. Prospective approval of Protocol deviations to recruitment and enrollment criteria, also known as Protocol waivers or exemptions, are not permitted.

5.1. Inclusion Criteria

Participants are eligible to be included in the study only if all of the following criteria apply:

- 1. Age ≥ 18 years.
- 2. A clinical diagnosis of nonsegmental vitiligo with depigmented areas including $\geq 0.5\%$ BSA on the face, ≥ 0.5 F-VASI, $\geq 3\%$ BSA on nonfacial areas, and ≥ 3 T-VASI; total body vitiligo area (facial and nonfacial) should not exceed 50% BSA.
- 3. At least 1 active vitiligo lesion (eg, such as confetti lesion, trichrome appearance, pinkish rim, or other evidence of inflammatory activity) at the site for skin biopsy.
- 4. Agree to discontinue all agents used to treat vitiligo from screening through the final safety follow-up visit. Over-the-counter preparations deemed acceptable by the investigator and camouflage makeups are permitted.

- 5. Willingness to take appropriate contraceptive measures to avoid pregnancy or fathering a child for the duration of study participation with the exception of the following:
 - a. Female participants of nonchildbearing potential (ie, surgically sterile with a hysterectomy and/or bilateral oophorectomy OR postmenopausal [≥ 12 months of amenorrhea without an alternative medical cause]).

Note: Information about specific types of acceptable contraceptive measures and duration of contraceptive use are provided in Appendix A.

6. Ability to comprehend and willingness to sign an ICF.

5.2. Exclusion Criteria

Participants are excluded from the study if any of the following criteria apply:

- 1. No pigmented hair within any of the vitiligo areas on the face.
- 2. Other forms of vitiligo (eg, segmental) or other differential diagnosis of vitiligo or other skin depigmentation disorders (eg, piebaldism, pityriasis alba, leprosy, postinflammatory hypopigmentation, progressive macule hypomelanosis, nevus anemicus, chemical leukoderma, and tinea versicolor).
- 3. Used depigmentation treatments (eg, monobenzone) for past treatment of vitiligo or other pigmented areas.

Note: Prior use of hydroquinone is not prohibited (because it is a bleaching agent, not a depigmentation treatment).

- 4. Concurrent conditions and history of other diseases:
 - a. Any other skin disease that, in the opinion of the investigator, would interfere with the study medication application or study assessments.
 - b. Active acute bacterial, fungal, or viral skin infection (eg, herpes simplex, herpes zoster, chickenpox) within 1 week before baseline.
 - c. Conditions at baseline that would interfere with evaluation of vitiligo.
 - d. Any serious illness or medical, physical, or psychiatric condition(s) that, in the investigator's opinion, would interfere with full participation in the study, including administration of study drug and attending required study visits; pose a significant risk to the participant; or interfere with interpretation of study data. Examples include but are not limited to the following:
 - Clinically significant or uncontrolled cardiac disease, including unstable angina, acute myocardial infarction within 6 months from Day 1 of study drug administration, New York Heart Association Class III or IV congestive heart failure, and arrhythmia requiring therapy or uncontrolled hypertension (blood pressure > 150/90 mmHg) unless approved by the medical monitor/sponsor.
 - History of thrombosis, including deep venous thrombosis and pulmonary embolism.
 - Concurrent malignant disease or a history of that in the 5 years preceding the baseline visit except for adequately treated nonmetastatic malignancies.

- Current and/or history of liver disease, including known hepatitis B or C, with hepatic or biliary abnormalities.
- Current and/or history of tuberculosis.
- History of alcohol use disorder or drug addiction within 1 year before screening or current alcohol or drug use that, in the opinion of the investigator, will interfere with the participant's ability to comply with the administration schedule and study assessments.
- Committed to an institution by virtue of an order issued either by the judicial or the administrative authorities.
- 5. Use of any of the following treatments within the indicated washout period before baseline:
 - a. 1 week: Topical drugs when used on the vitiligo areas, for example, corticosteroids, calcineurin, and phosphodiesterase type 4 inhibitors or retinoids.
 - b. 4 weeks:
 - Melanocyte-stimulating agents (eg, afamelanotide).
 - Immunomodulating systemic medications (eg, corticosteroids, methotrexate, cyclosporine).
 - Any other systemic therapies that could increase the skin sensitivity to UV/visible light or impact skin pigmentation, for example, tetracyclines, methoxypsoralens.
 - Received live vaccine.

Note: Live vaccine is prohibited during the course of the study and within 4 weeks after the EOT visit.

- c. 8 weeks: Laser or any kind of phototherapy, including tanning beds or intentional UV exposure.
- d. 5 half-lives or 12 weeks, whichever is longer: biologic agents, investigational or experimental therapy, or procedures for vitiligo. Investigational biologics should be discussed with the sponsor to determine whether a longer period of discontinuation is required.
- 6. Previously received JAK inhibitors, systemic or topical.
- 7. Investigator-determined clinically significant abnormal laboratory values at screening:
 - a. Hemoglobin (< 10 g/dL).
 - b. Liver function tests:
 - AST or $ALT \ge 2 \times ULN$.
 - Alkaline phosphatase and/or bilirubin > 1.5 × ULN (isolated bilirubin
 > 1.5 × ULN is acceptable if bilirubin is fractionated and direct bilirubin < 35%).
 - c. Severe renal disease (with creatinine clearance < 30 mL/min) or renal disease requiring dialysis.

- d. Clinically significant abnormal TSH or free T4 at screening as determined by the investigator.
- e. Positive serology test results at screening for HIV antibody.
- f. Hepatitis B virus or HCV infection: Participants who are positive for hepatitis B surface antigen or hepatitis B core antibody will be eligible if they are negative for HBV DNA; these participants should be considered for prophylactic antiviral therapy. Participants who are positive for anti-HCV antibody will be eligible if they are negative for HCV-RNA.
- 8. Body mass index $< 17 \text{ or} > 40 \text{ kg/m}^2$.
- 9. Pregnant or lactating, or considering pregnancy during the period of their study participation.
- 10. In the opinion of the investigator are unable or unlikely to comply with the administration schedule and study evaluations.
- 11. Employees of the sponsor or investigator or are otherwise dependents of them.
- 12. Known allergy or reaction to any component of the study formulation.
- 13. Live with anyone participating in any current Incyte-sponsored ruxolitinib cream study.

5.3. Lifestyle Considerations

Participants should be cautioned to avoid excessive exposure to artificial sunlight (including tanning beds, sun lamps, etc).

If sunscreen, makeup, or other cosmetics have been applied to the areas to be treated, participants should follow the application guidance (see Section 6.6.1).

It is recommended that swimming should not take place within 2 hours before and after the planned study drug application.

5.4. Screen Failures

Screen failures are defined as participants who consent to participate in the clinical study but are not subsequently randomly assigned to study treatment. Tests with results that fail eligibility requirements may be repeated once during screening if the investigator believes that the participant would be eligible if retested. Additionally, a participant who fails screening may repeat the screening process 1 time if the investigator believes that there has been a change in eligibility status or any laboratory abnormality is inconsistent with the participant's medical history. Participants who rescreen must reconsent and be assigned a new screening number.

5.5. Replacement of Participants

No participants will be replaced at any time during this study.

6. STUDY TREATMENT

See Appendix C for COVID-19–related guidance.

6.1. Study Treatments Administered

Table 6 presents the study treatment information.

Table 6:Study Treatment Information

	Ruxolitinib	Vehicle		
Study treatment name:				
MOA:	Inhibitor of the JAK family of protein tyrosine kinases	Not applicable		
Dosage formulation:	Cre	eam		
Unit dose strength(s)/dosage level(s):	1.5%	Not applicable		
Route of administration:	Topical			
Administration instructions:	A thin film is applied BID to depigmented vitiligo areas on the face and body up to 20% T-BSA.			
Packaging and labeling:	Ruxolitinib cream and vehicle cream will be provided in 60 g tubes. Each tube will be labeled as required per country requirement.			
Storage:	Ambient (15°C-30°C/59°F-86°F)			
Status of treatment in participating countries:	Investigational	Not applicable		

The application of study drug will be limited to $\leq 20\%$ of the participant's T-BSA, regardless of whether the participant has depigmentation on > 20% BSA. For participants with depigmentation on > 20% BSA, the investigator will discuss with the participant at baseline (Day 1) which areas of vitiligo to treat, and the areas selected for treatment must include all areas in which skin biopsies will be performed. The site should document the area to be treated in the eCRF.

All tubes of study drug will be weighed before being dispensed. All returned tubes of study drug will also be weighed.

Study drug will be applied as a thin film BID, with applications at least 8 hours apart. Participants should remove study drug from the tube in fingertip units until all of the areas to be treated are covered by a thin film.

Participants will be instructed to document treated areas and advised to limit use to no more than 1 tube (60 g) per 3-4 days. Application instructions will be provided by the site study staff, and the participants will record their daily applications via a diary card given to the participants during each study visit. Refer to the Study Pharmacy Manual for participant instructions for handling of study drug.

On the day of a visit, the participant should not apply their morning dose of study drug at home; instead, study drug will be applied from a new kit in the clinic during the visit, under direct supervision of the site staff. The tube will be weighed before and after application to determine the participant's dosage.

At any time during the study, if vitiligo areas become significantly more extensive than from the previous visit, the participant should contact the study site to discuss with the investigator whether additional evaluation at the clinic is required. If any other skin products that are permitted under the study Protocol are used, participants should continue these unchanged during the study.

6.1.1. Application During the Double-Blind, Vehicle-Controlled Treatment Period

During the double-blind, vehicle-controlled treatment period (up to Week 24), participants should follow the study drug application guidance below:

- Participants should apply study drug only to depigmented vitiligo areas identified by the investigators at baseline (Day 1) up to a T-BSA (facial and nonfacial) of $\leq 20\%$.
- Participants should continue to treat all depigmented vitiligo areas identified for treatment at baseline even if the area begins to improve or fully repigment.
- Participants who have an expansion of existing areas of vitiligo during the course of the double-blind period may treat these areas after a visit to document the VASI and other measures of vitiligo (may be an unscheduled visit), as long as the new treated T-BSA (facial and nonfacial) does not exceed 20% BSA.
- Participants who develop new vitiligo lesions during the course of the double-blind period should not treat these areas during the double-blind period. Newly developing vitiligo lesions should be documented in the eCRF, and the VASI for these new lesions should not be calculated and combined together with the area(s) to be treated identified at baseline.

6.1.2. Application During the Open-Label Treatment Extension Period

During the open-label treatment extension period (after Week 24), participants should follow the study drug application guidance below:

- Participants should apply study drug to depigmented vitiligo areas identified by the investigators at baseline (Day 1) up to a T-BSA (facial and nonfacial) of $\leq 20\%$.
- Participants should continue to treat all depigmented vitiligo areas identified for treatment at baseline even if the area begins to improve or fully repigment.
- Participants who have an expansion of existing areas of vitiligo during the course of the open-label period may treat these areas after a visit to document the VASI and other measures of vitiligo (may be an unscheduled visit), as long as the new treated T-BSA (facial and nonfacial) does not exceed 20% BSA.

• Participants who develop new vitiligo lesions during the course of study may treat these areas during the open-label period after a visit to document the VASI and other measures of vitiligo (may be an unscheduled visit), as long as the new treated T-BSA (facial and nonfacial) does not exceed 20% BSA. Newly developing vitiligo lesions should be documented in the eCRF and the VASI for these new lesions should not be calculated and combined together with the area(s) to be treated identified at baseline.

6.2. **Preparation, Handling, and Accountability**

The investigator or designee must confirm and document that appropriate temperature conditions (both ruxolitinib cream and vehicle cream are to be stored between 15°C and 30°C [59°F-86°F]) have been maintained during transit for all study drugs received and any discrepancies are reported and resolved before use of the study drug.

Only participants enrolled in the study may receive study drug, and only authorized site staff may supply study drug. Immediately after application of study drug, participants are to wash their hands thoroughly with soap and warm water (unless the area to be treated includes the hands). Refer to the Study Pharmacy Manual for participant instructions for handling of study drug.

All study drug must be stored in a secure, environmentally controlled, and monitored (manual or automated) area in accordance with the labeled storage conditions, with access limited to the investigator and authorized site staff. Participants should store study drug at ambient temperature conditions.

The investigator (or designee) is responsible for study treatment accountability, reconciliation, and record maintenance (ie, receipt, reconciliation, and final disposition records). Inventory and accountability records must be maintained and readily available for inspection by the study monitor and are open to inspection at any time by any applicable regulatory authorities. The investigator (or designee) must maintain records that document:

- Delivery of study drugs to the study site.
- Inventory of study drugs at the site.
- Participant use of the study drugs, including tube counts from each supply dispensed.
- Return of study drugs to the investigator or designee by participants.

The investigational product must be used only in accordance with the Protocol. The investigator will also maintain records adequately documenting that the participants were provided the specified study drug. These records should include dates, quantities, and any available batch or serial numbers or unique code numbers assigned to the investigational product and study participants.

Completed accountability records will be archived by the site. The investigator or designee will be expected to collect and retain all used, unused, and partially used containers of study drug until verified by the study monitor (unless otherwise agreed to by the sponsor). At the conclusion of the study, the investigator or designee will oversee shipment of any remaining study drug back to the sponsor or its designee for destruction according to institutional SOPs. If local procedures mandate on-site destruction of the investigational supply, the site should (where local procedures allow) maintain the investigational supply until the study monitor inspects the accountability records in order to evaluate compliance and accuracy of accountability by the investigative site. At sites where the study drug is destroyed before monitor inspection, the monitors rely on documentation of destruction per the site SOP.

Further guidance and information for the final disposition of unused study drugs is included in the study materials provided to sites.

6.3. Measures to Minimize Bias: Randomization and Blinding

All participants will be centrally assigned to study treatment using an IRT system. The system will assign study treatment in a 2:1 ratio (ruxolitinib cream 1.5% BID:vehicle BID), stratified by age (≤ 40 years old and > 40 years old). The IRT will assign participant ID numbers, track participant visits, randomize participants according to the defined parameters, maintain the blinding, and manage study drug inventory. Full details will be provided in the IRT Manual. Study treatment will be dispensed at the study visits summarized in the SoA (see Table 3 and Table 4).

After the database lock for the primary analysis, the sponsor will be unblinded, but investigators and participants will still be blinded to individual treatment assignments. This is implemented to minimize bias for the Week 52 analyses. After Week 52, investigators and participants will be unblinded.

6.4. Study Treatment Compliance

Compliance with all study-related treatments must be emphasized to the participant by the site personnel, and appropriate steps should be taken to optimize compliance during the study. Compliance with ruxolitinib cream or vehicle will be evaluated by participants' adherence to the application regimen and drug accountability documented by the site staff and monitored by the sponsor/designee (tube counts).

In general, the application compliance will be determined by the number of actual versus anticipated number of applications, which should be at least 70% but no more than 130% of the prescribed number of applications. Participants will be instructed to bring all study drug with them to the study visits in order for site personnel to conduct tube counts to assess study drug accountability. The drug accountability documentation will be used by the sponsor to calculate treatment compliance.

6.5. Dose Modifications

6.5.1. Criteria and Procedures for Dose Interruptions and Adjustments of Study Drug

Safety concerns should be discussed with the sponsor immediately upon occurrence or awareness to determine if the participant should continue or discontinue study treatment.

In some circumstances, it may be necessary to temporarily interrupt treatment with study drug. Except in cases of emergency, it is recommended that any findings of concern (eg, AE) be confirmed and that the investigator consult with the sponsor's medical monitor (or other representative of the sponsor) before interrupting study drug. Additionally, the investigator must obtain approval from the sponsor before restarting study drug. Participants who experience a recurrence of the initial AEs upon restarting the study drug may need the study drug to be permanently discontinued.

Instructions for application interruptions of study drug are outlined in Table 7. Individual decisions regarding interruptions should be made using clinical judgment in consultation with the medical monitor (whenever possible), taking into account relatedness of the AE to the study treatment and the participant's underlying condition.

Adverse Event	Action Taken
Chemistry	
ALT (> 3 × ULN) or AST (> 3 × ULN)	• Laboratory abnormalities should be confirmed with repeat testing within 48 hours whenever possible and immediate delivery of the laboratory results requested.
	• Study drug applications must be interrupted. At the discretion of the investigator, after consultation with the sponsor, study drug application may be restored once these have resolved.
Other laboratory abnormalities	
Any other Grade 3 laboratory abnormality, with the exception of asymptomatic elevations in triglyceride, cholesterol, or	• Laboratory abnormalities should be confirmed with repeat testing within 48 hours whenever possible and immediate delivery of the laboratory results requested.
amylase	• Study drug applications must be interrupted. At the discretion of the investigator, after consultation with the sponsor, study drug application may be restored once these have resolved.
Any Grade 4 laboratory abnormality or AST or ALT (> 5 × ULN)	• Laboratory abnormalities should be confirmed with repeat testing within 48 hours whenever possible and immediate delivery of the laboratory results requested.
	• Discontinue study drug if laboratory abnormalities are confirmed.

Table 7:	Guidelines for	Interruption and	d Restarting	of Study Drug
		1	0	

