7. DISCONTINUATION OF STUDY TREATMENT AND PARTICIPANT WITHDRAWAL

7.1. Discontinuation of Study Treatment

7.1.1. Reasons for Discontinuation

Participants **must** be discontinued from study treatment for the following reasons:

- A participant is found not to have met eligibility criteria (any exclusion criterion or any inclusion criterion related to participant safety) or if legal requirements have been violated.
- The participant becomes pregnant.
- Consent is withdrawn.

Note: Consent withdrawn means that the participant has explicitly indicated that he/she does not want to be followed any longer; in this case no further data, except data in the public domain, may be solicited from or collected on the participant. Participants may choose to discontinue study treatment and remain in the study for safety monitoring.

- Further participation would be injurious to the participant's health or well-being, in the investigator's medical judgment.
- Any AE of unacceptable severity as noted in Section 6.5.2.
- The study is terminated by the sponsor.
- The study is terminated by the local health authority, IRB, or IEC.

A participant **may** be discontinued from study treatment as follows:

- If, at 2 consecutive study visits, a participant's drug usage exceeds 1 tube (60 g) per 3-4 days.
- If a participant is noncompliant with study procedures or study drug administration in the investigator's opinion, the medical monitor should be consulted for instruction on handling the participant.

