8.3.5. Laboratory Assessments

Required clinical laboratory tests are listed in Table 8, which include hematology, chemistry, urinalysis, serology, free T4, TSH, FSH, and pregnancy testing, and will be performed as indicated in Table 3 and Table 4. Clinical laboratory tests will be performed at a central laboratory (refer to the Laboratory Manual for sample handling and shipping instructions).

Clinically significant abnormal laboratory findings are those that are not associated with the underlying disease, unless judged by the investigator to be more severe than expected for the participant's condition. All laboratory tests with values considered clinically significantly abnormal during participation in the study, or within 30 days after the last dose of study drug, should be repeated until the values return to normal or baseline or are no longer considered clinically significant by the investigator or medical monitor.

See Section 9.1 for information regarding laboratory abnormalities that should be recorded as an AE in the eCRF.

Serum Chemistries ^a	Hematology	Urinalysis With Microscopic Examination	Serology	Other		
Albumin Alkaline phosphatase ALT AST Bicarbonate or CO ₂ Blood urea nitrogen or urea Calcium Chloride Creatinine Glucose	Complete blood count, including: • Hemoglobin • Hematocrit • Mean corpuscular volume (MCV) • Platelet count • Mean platelet volume • Red blood cell count • Reticulocyte count • White blood cell count • Differential count, including: • Basophils • Eosinophils • Lymphocytes • Monocytes • Neutrophils	Color and appearance pH and specific gravity Bilirubin Glucose Ketones Leukocytes Nitrite Occult blood Protein	Hepatitis B surface antigen Hepatitis B core antibody Hepatitis B core immunoglobulin M antibody HCV antibody HCV-RNA (only performed if antibody positive) HIV antibody	FSH ^b Free T4 TSH		
Lactate dehydrogenase		Pregnancy Testing				
Phosphate Potassium Sodium Total bilirubin Direct bilirubin (if total bilirubin is elevated above ULN) Total protein		Female participants o serum test at the scree test will be conducted will be confirmed by	f childbearing potential ening and safety follow l at all other visits. A p a serum test.	will undergo a -up visits. A urine ositive urine test		

Table 8:Required Laboratory Analytes

Note: Additional tests may be required, as agreed upon by the investigator and sponsor, based on emerging safety data or to rule out a diagnosis.

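### Table 7 orders a hold for Grade 3 laboratory results but none for a non-transaminase Grade 4 result awaiting its repeat test

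*Protocol*

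**What the plan says.** Table 7 in Protocol section 6.5.1 has three rows of triggers and actions.

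- Row 1 covers ALT or AST above 3 × ULN. The result is to be repeated within 48 hours where possible, and "Study drug applications must be interrupted". Applications may resume after resolution, at the investigator's discretion and after consulting the sponsor.
- Row 2 covers "Any other Grade 3 laboratory abnormality, with the exception of asymptomatic elevations in triglyceride, cholesterol, or" amylase. Its actions are the same as in row 1.
- Row 3 covers "Any Grade 4 laboratory abnormality or AST or ALT" above 5 × ULN. The repeat-test instruction is the same, but the second action is "Discontinue study drug if laboratory abnormalities are confirmed".

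The text above the table applies to all rows. It says "Safety concerns should be discussed with the sponsor immediately upon occurrence or awareness". Outside emergencies, "it is recommended that any findings of concern (eg, AE) be confirmed and that the investigator consult with the" sponsor's medical monitor before interrupting drug. It requires sponsor approval before any restart, and it leaves individual interruption decisions to clinical judgment.

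Two other sections bear on the point. Section 7.1.1 makes discontinuation mandatory where "Further participation would be injurious to the" participant, in the investigator's judgment. Section 8.3.5 says clinically significant abnormal values "should be repeated until the values return to normal or baseline" or are no longer judged significant.

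**The concern.** A graded safety table should ask for at least as much at the worse grade as at the milder one, at every stage. On its wording, Table 7 does not. A Grade 3 platelet count carries an order to interrupt. A Grade 4 platelet count carries an order to repeat the test, with the stop depending on the outcome. Between first result and repeat, the written rule for the worse result contains no instruction to hold.

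What is at stake is uniform handling across sites. Hematology and chemistry are drawn at screening and at every visit (Tables 3 and 4). The uncovered group includes hematology results, and section 2.3 names thrombocytopenia, anemia and neutropenia as risks of oral ruxolitinib. Table 2 says there is no DSMB, so the site-level rule carries more of the load. No endpoint or statistical analysis is affected.

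**Working it through.** The plan gives no figure to reproduce. The check sets the rows side by side, looks elsewhere for a rule that fills the gap, and then sizes the gap.

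**1. The rows compared**

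| Row | Trigger | Repeat test | Action on drug | Conditional on confirmation? |
|---|---|---|---|---|
| 1 | ALT or AST > 3 × ULN | Yes, 48 h where possible | Interrupt | Not stated |
| 2 | Other Grade 3, with lipid/amylase exception | Same | Interrupt | Not stated |
| 3 | Any Grade 4, or AST/ALT > 5 × ULN | Same | Discontinue | Yes |

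Only row 3 makes its action depend on confirmation, and only row 3 has no interruption order.

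**2. Which results fall in the gap**

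- AST or ALT above 5 × ULN is also above 3 × ULN. Row 1 has no upper bound, so the hold already applies.
- A non-transaminase Grade 4 result does not meet row 2, which names Grade 3 alone and does not extend to higher grades.
- Protocol Table 10 and SAP section 9.3.2 provide separately for laboratory parameters with no CTCAE grade. The gap is therefore limited to Table 8 analytes that have a CTCAE Grade 4 definition, other than ALT and AST.

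**3. Whether another section supplies the hold**

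- 6.5.1, general text: permits a hold by judgment and asks for prompt sponsor contact. It orders no hold, and outside emergencies it favors confirming first.
- 6.5.2: has no laboratory criterion.
- 7.1.1: discontinuation is mandatory once participation is judged injurious, but that judgment is the trigger.
- 8.3.5: requires repeat testing, not a hold.

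None requires a hold for a pending, unconfirmed Grade 4 result.

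**4. Size of the gap**

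Inputs: twice-daily application (section 6.1); 48-hour repeat target (Table 7); 24-week double-blind period and 52 weeks of treatment in all (section 4.2: 24 + 28).

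- Applications in an on-time repeat window: 2 per day × 2 days = 4.
- Each further day of delay adds 2. With an assumed delay to day 7: 2 × 7 = 14. The documents give no actual turnaround, and row 3 asks for immediate delivery of results, so 14 is an illustration only.

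**5. Cost of a hold for a result that proves spurious**

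- Planned double-blind applications: 24 × 7 × 2 = 336; share missed: 4/336 = 1.2%.
- Planned applications over 52 weeks: 52 × 7 × 2 = 728; share missed: 4/728 = 0.5%.
- SAP section 6.5 defines intended applications as planned minus interrupted, so the held applications leave the denominator and calculated compliance does not fall.

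**The case against.** The strongest reply is that the table should be read with the text above it. That text recommends confirming findings before interrupting, except in an emergency, and in each row the repeat test is listed first and the drug action second. Read in that order, Grade 3 means confirm and then interrupt, while Grade 4 means confirm and then discontinue. No row then requires a hold during the repeat, and Grade 4 draws the stronger action.

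This reading is possible, and a site could follow it. It rests on a general recommendation, however, whereas rows 1 and 2 use mandatory wording with no condition and row 3 states one. A reader might infer that the protocol is less protective at the worse grade however it is read. The documents do not support that: the inversion exists on the table's own wording and disappears if confirmation comes first throughout.

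A second reply is that the rows are cumulative. Row 3 does not repeat the hold for AST/ALT above 5 × ULN, yet row 1 supplies it, so Grade 4 might be taken to carry the Grade 3 action too. Many sites would probably read it so. The wording does not say it, because row 2 is confined to Grade 3.

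A third reply is that safeguards exist, and this stands. The table is headed as guidelines. The confirm-first recommendation is lifted in an emergency, and section 9.3's fallback severity scale describes Grade 4 as life-threatening. Sponsor contact is immediate and results are to be delivered at once. These points make continued dosing unlikely, although they work through judgment and not through a stated hold.

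**Conclusion.** The point holds as a gap in a written safety rule. On its own wording, Table 7 orders interruption for ALT/AST above 3 × ULN and for most other Grade 3 results, but requires no hold while a non-transaminase Grade 4 result is being repeated. The size is up to 4 applications when the repeat is on time, plus 2 for each day it is late. This assumes twice-daily use as prescribed and a literal reading of the table.

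Two stronger inferences should be resisted. The protocol does not forbid a hold or direct sites to keep dosing at Grade 4; it leaves the matter to judgment. Nor does the gap reach every analyte in Table 8: ALT, AST and parameters with no CTCAE Grade 4 fall outside it.

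The practical risk is small. Section 2.3 does not expect clinically significant hematology changes with the cream, and the discretionary routes are likely to stop dosing. The documents give no Grade 4 rate, so no event probability is claimed. This is a cheap improvement for patient safety.

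**What to change.** Add one sentence to row 3 of Table 7: *Interrupt applications while the repeat result is pending; if the result is not confirmed, restart only with sponsor approval; if it is confirmed, discontinue.* The restart clause matches the approval already required in section 6.5.1.

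Widening row 2 to Grade 3 and above would be shorter but is not advised. A confirmed Grade 4 result would then fall under both row 2, which allows a restart after resolution, and row 3, which requires discontinuation, with no stated precedence.

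The change needs no new test or visit, because the repeat is already called for. Its downside is the roughly 4 missed applications for a participant whose Grade 4 result proves spurious.
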